11.3.2 Efficacy Analyses

CC/

11.3.3 Safety Analyses

AEs, laboratory, and vital signs will be summarized descriptively only within each of the 3 cohorts separately. No analysis combining data from 3 separate cohorts or comparing safety outcomes between cohorts will be performed.

If a subject is a non-responder at a certain infusion parameter level, AEs reported at the individually tolerable infusion parameter level after the non-response in the subject, ie, AEs starting at or after the next infusion following the infusion leading to non-response, will be listed and flagged, and analysed separately from the AEs reported prior to that time.

AEs will be summarized by the values of infusion parameters within each cohort. Rates per infusion will be presented as well. Adverse events will be presented including a virtual System Organ Class comprising local reaction (identified by the Medical Dictionary for Regulatory Activities high level terms: “administration site reactions NEC”, “infusion site reactions”, and “injection site reactions”) and by severity. Further, time to onset and duration will be presented descriptively. Tolerability of a certain infusion parameter within a cohort will be calculated as ‘number of infusions without severe local reaction / number of all infusions’ and be presented by infusion parameter and cohort. All infusions, regardless of the validity of the procedure (see Section 11.3.5) will be considered.

11.3.4 Pharmacokinetics and Pharmacodynamic Data

Not applicable.

11.3.5 Other Analyses – Infusion Parameters

For the primary endpoints, number and percentage of subjects with response will be provided.

If a subject is a non-responder at a certain infusion parameter level, data collected up to the time of non-response are taken into account for the analysis of response. Data collected at the individually tolerable infusion parameter level after the non-response in the subject will not be included in the analysis of response but will only be listed and flagged.

Percentages will be calculated as follows:

- a) An infusion will be considered ‘valid’ if the subject completes the full dose per scheduled infusion parameter (volume or flow rate) under test without interruptions or decrease during that infusion as detailed in [Table 6](#). Other protocol deviations may also lead to invalidation of an infusion. Protocol deviations will be treated on an infusion basis, not on a subject basis.

Table 6. Criteria for Valid Infusions

Cohort	Criteria for a valid infusion
Pump assisted volume cohort	
 Maximum volume administered per injection site is at least 95% of the planned maximum volume (ie, 25 mL, 40 mL or 50 mL) for at least one injection site and Infusion was not interrupted or stopped prematurely for any reason as documented in the eDiary and Total dose administered is at least 95% of the planned dose
Pump assisted flow rate cohort	
 Injection site flow rate is at least 95% of the planned flow rate (ie, 25 mL/h, 50 mL/h, 75 mL/h or 100 mL/h) for at least one injection site. and Infusion was not interrupted or stopped prematurely for any reason as documented in the eDiary and Total dose administered is at least 95% of the planned dose
Manual push cohort	
 The actual infusion duration is not more than 1 minute or 10% (whichever is larger) longer than the calculated infusion duration based on the desired flow rate (ie, 0.5 mL/min, 1 mL/min, or 2 mL/min) and the actual volume infused. and The actual infusion volume is at least 95% of the planned infusion volume for that infusion day.

- b) For the Pump-Assisted Cohorts, a subject is considered as a ‘responder’ for a certain infusion parameter if he/she has performed ≥ 3 valid infusions (see a) for that infusion parameter in any order, ie, not necessarily consecutive).
- c) For the Manual Push Flow Rate Cohort, a subject is considered as a ‘responder’ for a certain infusion parameter if he/she has performed $\geq k$ valid infusions (see a) for that infusion parameter in any order, ie, not necessarily consecutive) during the 4 weeks planned for that infusion parameter level, where k is specified in Table 7.

Table 7. Responder Requirements in Manual Push Cohort

Manual push infusions /wk	Infusions scheduled for parameter set (n)	Minimum No. of valid infusions (k)
2	8	5
3	12	7
4	16	10
5	20	12
6	24	15
7	28	17

- d) For each cohort (c) the percentage of subjects with response to a certain infusion parameter (p), $R_{c,p}$, will be calculated as [%]:
- $$100 * (\text{Number of responders for } p \text{ in cohort } c) / (\text{number of subjects from the Safety Population in cohort } c)$$
- where response is defined as outlined in b) and c), respectively.

The success criterion for any $R_{c,p}$ will be considered fulfilled if $R_{c,p} \geq 33\%$. Within each cohort, the highest infusion parameter with fulfilled success criterion will be considered the new top infusion parameter to be recommended for the Hizentra label. No formal statistical testing will be performed. All subjects included in the Safety Population of a cohort will be included in the denominator for calculation of $R_{c,p}$.

Rationale for number of valid infusions to qualify a responder in the manual push cohort: The probability for a subject to be a responder for a certain infusion parameter is assumed to be 50% irrespective of the value of the infusion parameter itself, ie, identical to the assumed response rate in [Section 11.1](#). This assumption is based on the expectation that there will be no infusion-related reasons for a subject to interrupt the infusion or change the infusion parameters. To achieve ≥ 3 out of 4 valid infusions the probability for a single infusion to be valid has to be $\geq 61\%$ for pump assisted cohorts. Using this 61% success probability for a single infusion in the manual push cohort the minimum of successes (k) in above table corresponds to a probability for a subject to be a responder of at least 50%.

The primary endpoints will be considered and evaluated independently from each other.

No imputation of missing data will be performed.

Descriptive subgroup analyses will be performed for Infusion Parameters by:

- Age class (≤ 17 years, > 17 years).
- BMI class ($< 30 \text{ kg/m}^2$, $\geq 30 \text{ kg/m}^2$).

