**Definition of valid infusions**

An infusion will be considered ‘valid’ if the subject completes the full dose per scheduled infusion parameter (volume or flow rate) under test without interruptions or decrease during that infusion. [Table 2](#) specifies for each cohort when an infusion is considered valid.

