**Table 2: Minimum criteria for a valid infusion**

Pump-Assisted Volume Cohort		
Infusion Parameter	Definition Per Protocol	Modified Definition
Volume	Maximum volume administered per injection site is at least 95% of the planned max volume (i.e., 25 mL, 40 mL or 50 mL) for at least 1 injection site.	No modification
Flow rate	Not applicable	Not applicable
Dose	Total dose administered is at least 95% of the planned dose.	No modification

Pump-Assisted Volume Cohort		
Interruptions or stops	Not interrupted or stopped prematurely for any reason as documented in the eDiary.	May be stopped for technical reasons* only.
AEs	Not addressed.	No related AEs started during interrupted or stopped infusion.
*Technical reason: technical problem with any part of equipment (pump, syringe, tubing, needle, including needle placement) used for infusion.		

Pump-Assisted Flow Rate Cohort		
Infusion Parameter	Definition Per Protocol	Modified Definition
Volume	Not applicable	Not applicable
Flow rate	Injection site flow rate is at least 95% of the planned flow rate (i.e., 25 mL/h, 50 mL/h, 75 mL/h, or 100 mL/h) for at least one injection site.	No modification
Dose	Total dose administered is at least 95% of the planned dose.	No modification
Interruptions or stops	Not interrupted or stopped prematurely for any reason as documented in the eDiary.	May be stopped for technical reasons* only.
AEs	Not addressed.	No related AEs started during interrupted or stopped infusion.
*Technical reason: technical problem with any part of equipment (pump, syringe, tubing, needle, including needle placement) used for infusion.		

Manual Push Flow Rate Cohort		
Infusion Parameter	Definition Per Protocol	Modified Definition
Volume	The actual infusion volume is at least 95% of the planned infusion volume for that infusion day.	No modification
Flow rate	The actual infusion duration is not more than 1 minute or 10% (whichever is larger) longer than the calculated infusion duration based on the desired flow rate (i.e., 0.5 mL/minute, 1 mL/minute, or 2 mL/minute) and the actual volume infused.	No modification

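### Flow rate cohort: a valid infusion needs the planned rate at only one site and no criterion covers a rate decrease, which conflicts with the plan's own definition and can bias the responder rate upward where sites have separate rates

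*Protocol*

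**What the plan says.** Protocol 11.3.5 first defines a valid infusion in a sentence: the full dose at the scheduled parameter, "without interruptions or decrease during that infusion as detailed in" Table 6. For the flow rate cohort, Table 6 then sets three conditions:

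- "Injection site flow rate is at least 95% of the planned flow rate", with the list of levels ending "75 mL/h or 100 mL/h) for at least one injection site";
- "Infusion was not interrupted or stopped prematurely for any reason as documented in the eDiary";
- "Total dose administered is at least 95% of the planned dose".

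A pump subject is a responder at a level if "he/she has performed ≥ 3 valid infusions" at that level.

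SAP 11.1 keeps both parts. Its introductory sentence has "under test without interruptions or decrease during that infusion", and the flow rate row of SAP Table 2 has "75 mL/h, or 100 mL/h) for at least one injection site". The per-protocol and modified definitions in SAP 2.2 use the same one-site condition and add the absence of prohibited medication. The modified definition changes the rule on stops and adds an adverse event condition, but leaves the flow rate condition alone.

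Protocol 14.4 states that an infusion must follow the predefined time, total volume and infusion rate, and that any departure makes it a failure for that level.

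SAP 8.2.8 derives the rate per site as the pump rate divided by the number of catheter branches, assuming equal flow in each. SAP Table 1 describes the level as a planned maximum rate per site.

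**The concern.** The general definition and Protocol 14.4 treat a reduced rate as disqualifying. No operative criterion does so. Lowering the rate is neither an interruption nor a premature stop, and the dose condition applies to the whole infusion, so a subject can meet all three conditions with only one site at the level.

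Lowering the rate at later sites is a plausible sign that the level was not well tolerated. If such infusions count as valid, the error runs in one direction, towards more responders at the higher rates. Validity drives the primary endpoint, and the highest level with a responder rate of at least 33% is the one to be recommended for the label (Protocol 11.3.5; 5 of 15 in Protocol 3.1). That is a small margin on which to leave the rule unsettled.

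**Working it through.** **The plan's own figure.** With 15 subjects and a true response rate of 50%, P(X ≥ 5) = 1 − (1 + 15 + 105 + 455 + 1365)/32768 = 1 − 1941/32768 = 0.941. The stated 94% reproduces. It takes the 50% as given, so the one-site rule does not alter it. What changes is who counts as a responder.

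**The passages side by side, for an infusion with one site at the level and another below it.**

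| Text | Result |
|---|---|
| Protocol Table 6; SAP 2.2; SAP Table 2 | Valid, if not interrupted and 95% of the dose is given (in SAP 2.2, also no prohibited medication) |
| Introductory sentence, Protocol 11.3.5 and SAP 11.1 | Not valid, if the lower rate is a decrease during the infusion |
| Protocol 14.4 | Not valid, if the lower rate departs from the predefined rate |

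**When the case can arise.** Take one pump feeding m branches at a constant rate. SAP 8.2.8 gives every branch the value pump rate/m, so all branches pass or all fail, and the one-site and all-site rules agree. They can differ only if sites have separately recorded rates. The plan leaves room for this: SAP 8.2.8 lists a straight catheter, which feeds one site, and derives volume from what a specific pump delivered.

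A rate turned down partway on a single pump is a separate gap. Protocol 6.2.2 takes the rate from the pump display and SAP 8.2.8 from the diary. Neither says whether the initial, highest or final reading is used.

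**What one such infusion looks like (invented example).** Two 25 mL sites in sequence, the first at 100 mL/h:

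- second at 25 mL/h: 50/(25/100 + 25/25) = 50/1.25 = 40 mL/h on average;
- second at 50 mL/h: 50/(25/100 + 25/50) = 50/0.75 = 66.7 mL/h on average.

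Both pass Table 6 for 100 mL/h. With four equal sites, 3/4 = 75% of the dose could run below the level. By contrast, the manual push criterion tests the whole infusion by its duration. The first example takes 15 + 60 = 75 minutes against a calculated 30, beyond a 10% allowance (33 minutes).

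**Weight of one subject.** 1/15 = 6.7 points; 5/15 = 33.3% meets the criterion and 4/15 = 26.7% does not.

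**How far the rules can diverge (illustration only).** Assume every infusion uses m = 2 separately recorded sites, each reaching the level independently with probability q, and take one level in isolation. One-site validity is v = 1 − (1 − q)², and all-site validity is v = q². Responder probability is 4v³(1 − v) + v⁴, and cohort success is P(at least 5 of 15).

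| q | Valid: one-site / all-site | Responder: one-site / all-site | Cohort success: one-site / all-site |
|---|---|---|---|
| 0.61 | 84.8% / 37.2% | 88.8% / 14.9% | >99.9% / 6.0% |
| 0.75 | 93.8% / 56.3% | 97.8% / 41.2% | >99.9% / 80.9% |
| 0.90 | 99.0% / 81.0% | 99.9% / 83.4% | >99.9% / >99.9% |

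The documents give neither q nor the number of sites. Sites within a subject are unlikely to be independent, and the more alike they are, the closer the two rules come. With m = 1 they coincide. Depending on q, the divergence may or may not change the cohort decision.

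**The case against.** The strongest reply is that the texts, read together, already exclude the case. The introductory sentence bars a decrease, SAP Table 2 is headed as a list of minimum criteria, and Protocol 14.4 disqualifies departures from the rate. This does not settle the matter. The introductory sentence refers to Table 6 for its detail, and no row there implements the word decrease. SAP 11.1 says that Table 2 specifies when an infusion is valid, and it ties failure to its own criteria rather than repeating Protocol 14.4. A programmer working from the tables would count the infusion as valid.

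Other points on that side stand:

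- SAP Table 1 speaks of a maximum rate per site, so the one-site wording may be deliberate. A site planned at a lower rate from the start is not plainly a decrease.
- Protocol 4.1.1 recognises constant-pressure pumps, whose flow depends on needle and tubing, and accepts ±20% of 25 mL/h at entry. A 95% rule at every site could fail some infusions for equipment reasons. This weighs against simply replacing the primary rule.
- A responder needs at least three valid infusions at the level, so the pattern must recur.

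A reader might also infer that the rule credits adverse reactions to a rate at which most of the dose was not given. The documents do not support that as an effect of validity: Protocol 11.3.3 and SAP 11.4 calculate tolerability from all infusions irrespective of validity, and SAP 11.4 does the same for adverse event rates.

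**Conclusion.** The inconsistency is real and concerns the primary endpoint. The operative flow rate criteria are looser than the plan's general definition and than Protocol 14.4. Where sites have separately recorded rates, the responder rate can be biased upward.

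A reader might go further and infer that any subject who slows the other sites is counted as a responder, or that the reported rates will be inflated. The documents do not support either. With one pump at a constant rate the one-site and all-site rules give the same answer, and the frequency of the other case is not stated. The table under the working shows what is possible under assumed inputs; it is not an estimate. The firm quantities are that one subject is 6.7 points at n = 15 and that the decision turns on 5 versus 4 responders. That is enough to justify settling the rule before the data are analysed.

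**What to change.** 1. Reconcile Protocol 11.3.5 (introductory sentence and Table 6), Protocol 14.4, SAP 2.2 (both definitions), and SAP 11.1 with its Table 2. For the flow rate cohort, state whether every separately recorded site must reach 95% of the planned rate, whether a recorded reduction invalidates the infusion, and which pump reading is used. The volume cohort's one-site wording can stay, since one site may receive only the remainder of the dose.
2. If the one-site rule stays primary, add a supportive responder rate requiring all recorded sites to be at least 95% of plan, with the number of infusions on which the two rules differ. A count of zero closes the question.
3. To detect reductions within an infusion, add a yes/no diary item if none exists.

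The cost is a few phrases and one table row. Protocol 9.7.1 already has volume, location and infusion rate recorded, so step 2 should need no new data. Step 3 is dearer: the diary screens cited by the SAP date from March 2017 and the SAP from July 2018, so a new item would cover only infusions still to come. The drawback of a stricter rule is a somewhat lower responder rate, with some infusions failing because of constant-pressure pumps rather than intolerance. Reporting it as supportive limits that.

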6.2.2 Infusion Rates

For pump-assisted infusions, the volume and flow rate will be determined according to the pump display readings. As it is physically not possible to perform manual push at a constant rate, and it is performed in clinical practice by series of short manual pushes on the syringe plunger with small breaks between them, average flow rate per infusion in this cohort will be estimated by dividing volume infused in milliliters by the time of infusion in minutes.

The subject electronic diary (eDiary) for study participants in the Manual Push Cohort will provide recommendations of infusion duration depending on the actual dose (volume) to be infused and the target flow rate in mL/min for every subject using the following calculations (Table 2). If the eDiary is not available, a back-up paper diary will be provided for patient use until the eDiary becomes available. As soon as the eDiary is available, the data in the back-up paper diary will be entered into the eDiary. The back-up paper diary, if used, will be retained as a source document. During the time period when a back-up paper diary is in use, designated site staff will contact the subject on a weekly basis to ensure recording of infusion data and any AEs.

Table 2. Infusion Time

Volume, mL \ Flow rate, mL/min	0.5	1	2
	Infusion Time, minutes		
2	4	2	1
3	6	3	1.5
4	8	4	2
5	10	5	2.5
6	12	6	3
7	14	7	3.5
8	16	8	4
9	18	9	4.5

Flow rate, mL/min Volume, mL	0.5	1	2
10	20	10	5
11	22	11	5.5
12	24	12	6
13	26	13	6.5
14	28	14	7
15	30	15	7.5
16	32	16	8
17	34	17	8.5
18	36	18	9
19	38	19	9.5
20	40	20	10

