Manual Push Flow Rate Cohort	
 
• The actual infusion duration is no more than 1 minute or 10% (whichever is longer) longer than the calculated infusion duration based on the desired flow rate (i.e., 30 mL/h [0.5 mL/min], 60 mL/h [1 mL/min], or 120 mL/h [2 mL/min]) and the actual volume infused and
 
• No prohibited concomitant medication and
 
 
The actual infusion volume is at least 95% of the planned infusion volume for that infusion day over all infusion sites.
																					
Definition of Responder per Infusion Parameter Level																						
Pump-Assisted Volume Cohort	≥ 3 valid infusions in any order (out of 4 infusions)																					
Pump-Assisted Flow Rate Cohort	≥ 3 valid infusions in any order (out of 4 infusions)																					
Manual Push Flow Rate Cohort	
≥ k valid infusions in any order during the 4 weeks planned for that infusion parameter level, with k being
 
  
 Manual push infusions per week	Total number of infusions scheduled for parameter set	Minimum number of valid infusions (k)	
   
 2	8	5	
 
 3	12	7	
 
 4	16	10	
 
 5	20	12	
 
 6	24	15	
 
 7	28	17	
  
	Manual push infusions per week	Total number of infusions scheduled for parameter set	Minimum number of valid infusions (k)	2	8	5	3	12	7	4	16	10	5	20	12	6	24	15	7	28	17
Manual push infusions per week	Total number of infusions scheduled for parameter set	Minimum number of valid infusions (k)																				
2	8	5																				

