### 3 Purpose

This SAP provides a detailed and complete description of the planned statistical analyses for the final analysis of the study IgPro20\_4004 to support the Clinical Study Report (CSR). Mock tables, figures, and listings (TFLs) shells are provided in separate supporting documents.

This SAP complies with the International Conference on Harmonization (ICH) Harmonized Tripartite Guideline Topic E9, Statistical Principles for Clinical Trials. It is based upon the following study documents:

- Study Protocol (dated 15 Aug 2016);
- Study Protocol Amendment 1 (dated 1 Feb 2017);
- Study Protocol Amendment 2 (dated 31 May 2017);
- Study protocol Amendment 3 (dated 2 Dec 2017);
- Annotated electronic Case Report Form (eCRF) (dated 02 Feb 2017);
- Annotated eCRF (dated 29 Jan 2018);
- Annotated eCRF (dated 26 Jun 2018);
- Screen Report for eDiary (dated 14 Mar 2017).

All decisions regarding the final analysis of the study results, as defined in this SAP document, have been made prior to Database Freeze of the study data.

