### **Formatting for Dates and Times**

- Dates only – ddmmmyyyy;
- Times only – hh:mm or hh:mm:ss (as appropriate);
- Dates and times – ddmmmyyyy hh:mm or ddmmmyyyy hh:mm:ss (as appropriate).

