**Calculation of percentage of responder**

The percentage of subjects with response  $R_{c,p}$  in cohort  $c$  to a certain infusion parameter  $p$ ,  $R_{c,p}$ , will be calculated as:

$$R_{c,p}(\%) = \frac{100 * (\text{Number of responder for } p \text{ in cohort } c)}{\text{Number of subjects in the SAF for cohort } c}$$

where response is defined as outlined above.

The success criterion for any  $R_{c,p}$  will be considered fulfilled if  $R_{c,p} \geq 33\%$ .

Within each cohort, the highest infusion parameter with fulfilled success criterion will be considered the new top infusion parameter to be recommended for the Hizentra® label. No formal statistical testing will be performed.

All subjects included in the SAF of a cohort will be included in the denominator for calculation of  $R_{c,p}$ .

Number of infusions and number and percentage of valid infusions and number and percentage of responder will be presented by cohort and infusion parameter level. The base for the percentages will be the number of infusions and the number of subjects within the cohort.

Subgroup analyses for

- Age class ( $\leq 17$  years,  $> 17$  years) and
- BMI class ( $< 30$  kg/m^2,  $\geq 30$  kg/m^2)

will be produced (Table 14.3.2).

A by-subject listing with the information as described in Section 7 as well as start and end date and time of infusion, depending on the cohort and planned infusion parameter level: actual parameter level and percentage of planned and for manual push actual infusion duration and calculated infusion duration, for all cohorts: infusion interrupted or stopped, prohibited concomitant medication administered, validity of the infusion, and responder (no/yes) will be provided. In this listing, the data which is collected after a subject has been classified as non-responder will be flagged.

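### At the 120 mL/h manual-push level, the 1-minute allowance accepts small infusions averaging as little as 60 mL/h (2 mL) to 86 mL/h (5 mL), and the SAP text plans no summary of achieved rates

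*Protocol*

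**What the plan says.** Protocol 11.3.5, Table 6, accepts a manual-push infusion if "The actual infusion duration is not more than 1 minute or 10% (whichever is larger) longer than the calculated infusion duration" for the target rate and the volume actually given, and if at least 95% of the planned volume is given. SAP 11.1, Table 2, repeats this. SAP 2.2 also has a Modified Definition, which relaxes the pump rules for technical stops. For manual push it keeps the same limit: "The actual infusion duration is no more than 1 minute or 10% (whichever is longer) longer than the calculated infusion duration".

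Protocol 6.2.2 explains that manual push cannot be done at a constant rate, and says that "average flow rate per infusion in this cohort will be estimated by dividing volume infused in milliliters by the time of infusion in minutes".

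Protocol 14.4 is stricter in wording. It treats an infusion as valid when it keeps to the time, volume and rate laid down in advance, and counts any departure as a failure. The matching paragraph of SAP 11.1 instead counts departures from the Table 2 criteria.

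SAP 11.1 tabulates counts and percentages of infusions, valid infusions and responders. A by-subject listing gives "actual parameter level and percentage of planned and for manual push actual infusion duration and calculated infusion duration". SAP 10.2 and 11.3 summarise dose and volume, not rate. SAP 3 says that the table, figure and listing "shells are provided in separate supporting documents"; these were not available for this review.

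The result has a direct use. Taking the cohorts separately, "the highest infusion parameter with fulfilled success criterion will be considered the new top infusion parameter to be recommended for the Hizentra label", with success set at a responder percentage of 33% or more.

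**The concern.** A fixed 1-minute allowance is large when the calculated time is itself only 1 to 3 minutes. For the smallest infusions the rule may then fail to separate the tested level from the level below it. In the same table the pump flow-rate cohort must reach 95% of the planned rate.

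The column labelled Other in SAP 11.1 does not catch this. It is for infusions that fail the planned-level criteria, so a slow infusion accepted under the allowance stays in the 120 mL/h column. If small-volume subjects contribute to a 120 mL/h result, the tables as described would not show whether their valid infusions ran near 120 or near 60 mL/h. The age-class subgroup shows who responded, not at what rate.

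Small volumes are possible under the plan. Protocol Table 2 starts at 2 mL, up to 7 infusions a week are allowed, and pediatric subjects may enter any cohort (Protocol 3.5).

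**Working it through.** **Inputs.** Tolerance: Protocol Table 6 and SAP Table 2. Calculated times: Protocol Table 2. Scheduled infusions n and required valid infusions k: Protocol Table 7. Dose usually 100 to 200 mg/kg per week: Protocol 3.2. Content 200 mg/mL: SAP 11.3. Fifteen subjects per cohort, assumed response 50%, threshold 33%: Protocol 11.1 and 11.3.5.

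**1. The plan's own figures.** Volume V divided by rate r (mL/min) reproduces all 57 cells of Protocol Table 2; at 2 mL/min, 2 mL takes 1 min, 5 mL takes 2.5 min and 20 mL takes 10 min. The stated 94% also reproduces: P(X ≥ 5) for a binomial with n = 15 and p = 0.5 is 0.941.

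**2. Which allowance governs.** At 2 mL/min, 10% of the calculated time is 0.05V minutes. This is under 1 minute for V < 20 mL and equals it at 20 mL.

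**3. Slowest accepted average rate (mL/h)** = 60V / (V/r + max(1, 0.1V/r)). At r = 2:

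| Volume (mL) | Calculated (min) | Longest valid (min) | Slowest rate (mL/h) | % of 120 |
|---|---|---|---|---|
| 2 | 1 | 2 | 60 | 50 |
| 3 | 1.5 | 2.5 | 72 | 60 |
| 4 | 2 | 3 | 80 | 67 |
| 5 | 2.5 | 3.5 | 85.7 | 71 |
| 6 | 3 | 4 | 90 | 75 |
| 10 | 5 | 6 | 100 | 83 |
| 20 | 10 | 11 | 109.1 | 91 |

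Two minutes for 2 mL is exactly Protocol Table 2's time at 1 mL/min (60 mL/h). Up to 5 mL the floor is nearer to 60 than to 120. At the mean volumes per site in Protocol 1.1.4 the floors are 948/8.9 = 106.5 mL/h (15.8 mL, adults), 1026/9.55 = 107.4 (17.1 mL, ages 10 to 18) and 1068/9.9 = 107.9 (17.8 mL, obese adults). At the 60 mL/h level only 2 mL (120/3 = 40 mL/h) falls below 45 mL/h, the midpoint with the 30 mL/h level; 3 mL gives 180/4 = 45.

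**4. Who gives less than 6 mL.** Assuming the weekly dose is split equally, the limiting weight is 6 × f × 200 / d, with f infusions per week and d mg/kg per week.

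| Infusions/week | d = 100 | d = 150 | d = 200 |
|---|---|---|---|
| 7 | 84 kg | 56 kg | 42 kg |
| 5 | 60 kg | 40 kg | 30 kg |
| 3 | 36 kg | 24 kg | 18 kg |
| 2 | 24 kg | 16 kg | 12 kg |

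The 2 mL case is much narrower. At 7 per week it needs at most 2 × 7 × 200 / d = 28 / 18.7 / 14 kg.

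**5. From infusion to responder.** Take a floor of 90 mL/h, midway between 60 and 120. A subject whose infusions are all valid under Table 6 loses responder status only if n − k + 1 of them fall below it: 4 of 8, 6 of 12, 7 of 16, 9 of 20, 10 of 24 or 12 of 28 (2 to 7 per week). A subject with exactly k valid infusions needs only one.

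**6. From responder to conclusion.** With 15 subjects, 5/15 = 33.3% passes and 4/15 = 26.7% fails. One lost responder changes the conclusion only if exactly 5 respond. At the assumed 50% (7 or 8 responders), 3 or 4 must be lost.

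**7. Rounding.** An infusion passes Table 6 but fails 90 mL/h if 2V/3 < t ≤ V/2 + 1: over 1.33 up to 2 min at 2 mL, over 2 up to 2.5 at 3 mL, over 2.67 up to 3 at 4 mL, over 3.33 up to 3.5 at 5 mL, and never at 6 mL. For whole-mL volumes and whole-minute durations, only 2 mL in 2 min and 4 mL in 3 min are affected.

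**The case against.** The strongest reply is that the tolerance is reasoned and the exposure small. Manual push consists of short pushes with pauses, so an average rate must run below the pushing rate. The eDiary recommends the target duration, so the floors are not expected rates. The published mean for ages 10 to 18 is 17.1 mL, where the floor is about 90% of target; being pediatric does not by itself imply a small volume. Protocol Table 2 is a look-up of times, not a forecast of volumes. The SAP's week-mapping table (section 7) has columns only for 2 to 5 infusions per week, although up to 7 are allowed. A listing for about 15 subjects can be read by eye, and the unseen shells may already include a rate table.

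Most of this stands, and it limits the size of the point. It does not explain why the floor at 2 mL should equal the next lower tested level, and a listing is not a planned summary.

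A reader might infer that a 120 mL/h label recommendation would rest on infusions given near 60 mL/h. The documents do not support that: they give no distribution of volumes or achieved rates, and several subjects would usually have to change status. Nor can one say that nothing in the plan constrains the rate more tightly, because Protocol 14.4 does so in words.

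**Conclusion.** The concern holds as a minor one. As written, the rule lets infusions below 6 mL count for 120 mL/h at average rates nearer to 60 mL/h, and at 2 mL it does not separate the two levels. Protocol 14.4 conflicts with the Table 6 tolerance, and the two must be reconciled.

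The arithmetic is exact; the consequence is uncertain. It depends on how many subjects repeatedly give less than 6 mL and run close to the time limit, which the documents do not say. The weight limits assume equal division of the weekly dose within the usual range, and the responder counts assume 15 subjects in the cohort. The finding that no summary of achieved rate is planned rests on the SAP text alone.

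**What to change.** Leave Table 6, progression between levels and the success criterion unchanged, and reconcile Protocol 14.4 with Table 6. In SAP 11.1:

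- For valid manual-push infusions, tabulate achieved mL/h (volume over time, as in Protocol 6.2.2), percentage of target and volume per infusion, by level.
- State the time resolution of recorded infusion durations. SAP section 7 allows times to be shown with or without seconds.
- Add a supportive responder percentage that also requires the achieved rate to be at least as close to the tested level as to the level below: 90 mL/h for 120 and 45 mL/h for 60. These are sensitivity cut-offs chosen here, not values from the documents.
- Label it separately, outside the Modified Definition column. SAP 11.1 presents both definitions without saying which decides the label. They are identical for manual push now, and a stricter rule in that column would make them differ.
- State that the per-protocol definition alone decides the label recommendation, and report whether the 33% conclusion differs.

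The cost is one SAP paragraph, one derived variable from data already collected, one descriptive table and one more analysis. The supportive percentage can only be equal to or lower than the primary one. At 2 to 5 mL it is sensitive to rounding of durations, so it should inform interpretation and not decide anything.
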